10.2 Source Documents

Source data and source documents will be stored on BMC secure servers. They include study team administrative notes, study clinician notes and progress checklists, recorded data from automated instruments including REDCap, audio files and audio transcription documents. Data generated by the methods described in the protocol will be recorded in the subjects' study progress notes.

10.3 Case Report Forms

CRFs will not be used for this study. All data will be saved in REDCap, most of which will be inputted by participants themselves.

10.4 Study Records Retention

All records will be saved on BMC's secure servers electronically and retained at least seven years after completion of the study. At the completion of the study, any paper notes will be scanned and uploaded as electronic documents to the BMC server. Within the informed consent process, participants indicate whether their audio recordings can be used for research and teaching purposes. Examples on how they may be used include during training new study staff on the measure or used as an example during a research presentation. Audio recordings of participants who say that their recordings can be used will be retained and others will be deleted at the end of the study. Any identifying information disclosed within the audio files will be removed by editing, the files themselves are de-identified.

11 Statistical Plan

11.1 Study Hypotheses

1. The MILO intervention will be feasible and acceptable for participants.
2. The MILO intervention will impact outcomes of interest (e.g., proficiency using MILO skills, confidence, stress, caregiving attitudes, and caregiver-reported IP treatment engagement).
3. Participants attending MILO sessions will show more improvement with regard to outcomes of interest within the first six weeks of study participation relative to those on the waitlist.
4. After attending MILO sessions, waitlisted participants will “catch up” to those randomized to receive the intervention immediately with regard to changes on outcomes of interest.
5. Gains in MI proficiency as demonstrated via scored audio recordings will mediate the impact of the intervention on other outcomes such as reduced conflict and stress and increased confidence and caregiver-reported IP treatment engagement.

11.2 Sample Size Determination

The overall target for recruitment is 100 participants. 52 participants will be recruited for the protocol once approved by BMC (48 participants were recruited at Beth Israel Deaconess Medical Center which was the original recipient of the K23 funding support). This study is a pilot intended to test feasibility and preliminary effectiveness of the MILO intervention. Although true “pilot” studies focus an on intervention’s feasibility, rather than effects per se, the current study reflects a two-phase hybrid of priorities balancing the need to focus on feasibility while also investigating whether the intervention impacts the hypothesized treatment targets (MI skills, self-efficacy) and whether it is more effective in achieving the primary outcome (IP engagement in FEP treatment) than a control condition representing “treatment as usual” and a waiting period. The control group will be small relative to the active treatment group, thus maximizing the feasibility-focused sample. Thus the study may be somewhat underpowered to detect statistically significant effects, but has been designed to yield high quality feasibility metrics, highlight important factors for implementation, and provide a rough estimate of effect size that will inform a later, fully powered RCT.

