4.2.2 Secondary Outcome Measures

Measurement of secondary outcomes will occur using the instruments in the table below.

Measure	Study Objective	Time Point
Absolute Worth and Autonomy Scale	Aim 2b: Reducing distress among PCSO	Baseline, Waitlist Condition, Post Intervention, 8 Week FU, 12 Week FU
Perceived Stress Scale	Aim 2b: Reducing distress among PCSO	Baseline, Waitlist Condition, Post Intervention, 8 Week FU, 12 Week FU
Conflict Behavior Questionnaire	Aim 2b: Reducing distress among PCSO	Baseline, Waitlist Condition, Post Intervention, 8 Week FU, 12 Week FU
SCORE-15 Index of Family Functioning	Aim 2b: Reducing distress among PCSO	Baseline, Waitlist Condition, Post Intervention, 8 Week FU, 12 Week FU
Parenting Self Agency	Aim 2b: Reducing distress among PCSO	Baseline, Waitlist Condition, Post Intervention, 8 Week FU, 12 Week FU
Family Questionnaire	Aim 2b: Reducing distress among PCSO	Baseline, Waitlist Condition, Post Intervention, 8 Week FU, 12 Week FU
Motivational Interviewing Skills Questions	Aim 2a: Feasibility	Baseline, Post- Intervention
Mental Health Service Use History	Aim 2a: Facilitating engagement of IP in treatment	Baseline
Past Month Service Use History	Aim 2a: Facilitating engagement of IP in treatment	Baseline, Waitlist Condition, Post Intervention, 8 Week FU, 12 Week FU
Change Questionnaire	Aim 2b: Reducing distress among PCSO	Post Intervention, 12 Week FU

10 Minute Audio Recorded Role Play	Aim 2a: Feasibility	Baseline, Waitlist Condition, Post Intervention
------------------------------------	---------------------	---

5 Study Design

[figure not shown]
The study population is parents and concerned significant others (PCSO) of individuals experiencing psychosis (IP) who are not currently engaged with treatment. The IP has to have a recent onset of psychosis within the past 5 years. MILO is a structured brief intervention that seeks to accomplish two aims. The primary aim is to facilitate the engagement of IP with evidence-based treatments. The secondary aim is to reduce the distress and increase the wellbeing of PCSO. The intervention will be trialed for feasibility and then tested against a small waitlist condition control arm. Participants will be randomly assigned to either receive MILO (50%) or the waitlist condition (50%) in a cross over design.

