The study is designed to minimize participant burden. Concerns about the ethics of randomization are allayed by the fact MILO is untested (effectiveness is not proven), and that the control condition represents treatment as usual. Thus the risk benefit ratio, even for those assigned to “treatment as usual/waitlist”, is favorable given that typically no particular assistance is offered in the community for parents/significant others attempting to connect their loved one with care. Phase 1 of the study was completed at its initial site at Beth Israel Deaconess Medical Center. Phase 2 was also started at the previous sight and will be completed at Boston Medical Center.

We will be collecting data through REDCap surveys administered via email link to the participants. Those assigned to the MILO treatment condition will be assessed at 4 time points (study entry, post intervention, 8 week follow up, 12 week follow up). Those in the waitlist condition will be assessed at 5 time points (study entry, end of waitlist, post intervention, 8 week follow up, 12 week follow up). Please see the following measures:

- Participants Contact Information
- Demographics questionnaire
- SCID-5 Adjustment disorder module
- Absolute Worth and Autonomy Scale
- Perceived Stress Scale
- Conflict Behavior Questionnaire
- SCORE-15 Index of Family Functioning
- Parenting Self-Agency
- Family Questionnaire
- Motivational Interviewing Skills Questions
- Mental Health Service Use History & Past month Service Use History Forms
- Modified Client Satisfaction Questionnaire
- Change Questionnaire

- 10-minute audio-recorded standardized patient role play (at study entry and post-intervention and waitlist time points only; role-plays will be scored using the Motivational Interviewing for Loved Ones Skills Assessment.

6 Potential Risks and Benefits

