Consent	If potential participant is eligible, they are offered a time to review the study consent with study staff. Once study details have been reviewed and study staff have made sure participants have no lasting questions, then study staff send the REDCap consent link to the participants. Participants are given study staff contact information if they have any more questions before signing the document via REDCap. If participants do not have access to necessary technology to complete a remote consent, they will be invited to [name] office. All in person operations will follow BMC's COVID procedures.
Baseline Assessments	Participants are sent a REDCap survey link after consent is complete via email and asked to schedule a 15 minute phone call with study staff to complete their baseline real play assessment
Randomization	Once baseline assessments are complete, study staff randomize participant into MILO or waitlist condition.
IF Waitlist Condition	Participants randomized to waitlist condition, are emailed the date that their waitlist period ends and offered a 30 minute treatment consultation with one of the MILO trainers before the 6 week waitlist period is complete. This treatment consultation can be completed over the phone, over a BMC Zoom, or in person at [name] office. All in person visits will follow BMC's COVID procedures. At the end of the waitlist period, they are sent REDCap surveys and asked to complete another real play assessment over the phone (first done at baseline).
MILO Treatment	Participants randomized to immediate MILO, as well as those who have already finished the waitlist period, are scheduled for their first MILO training session. Sessions are offered via a secure telehealth platform, HIPAA compliant Zoom or in person if the participant does not have access to appropriate technology. All in person operations will follow BMC's COVID procedures. Sessions are 45-60 minutes and participants are offered 4-5 sessions. All sessions are conducted by trained study staff. Study staff receive weekly individual supervision from the PI.

	Study staff utilize detailed guides to ensure high fidelity to the MILO intervention. Details of the intervention are described in the table above in section 8.
Post-Intervention Assessments	Once participants have completed MILO intervention, they are emailed their post-intervention REDCap survey and asked to schedule their last real play audio recorded exercise over the phone.

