11.3 Statistical Methods

Feasibility will be analyzed using the following descriptive metrics: # participants screened; # Eligible; # Enrolled; # not enrolled and corresponding reasoning # Meeting DSM-5 Adjustment Disorder criteria; Percentage of Treatment sessions completed; Treatment Satisfaction; % assessments completed; Duration of assessments.

The outcomes of interest will be compared between the intervention and waitlist groups, and also within the waitlist group (comparing the pre-post intervention changes to the pre-post waitlist time changes. Prevalence of IP treatment seeking in each group will also be analyzed via odds ratios. Secondary outcomes, i.e. changes in PCSO distress and quality of life, will be

assessed via repeated measures ANOVAs examining group-by-time changes. Similarly, hypothesized mediators of effects (MI skill proficiency and self-efficacy) will be examined via repeated measures ANOVAs examining group-by-time changes. Analyses will be conducted using SPSS software.

12 Ethics/Protection of Human Subjects

This study is to be conducted according to applicable US federal regulations and institutional policies (which are based in federal regulations, guidance, and ICH Good Clinical Practice guidelines).

This protocol and any amendments will be submitted to the Boston Medical Center and Boston University Medical Campus IRB, for formal approval of the study conduct. The decision of the IRB concerning the conduct of the study will be made in writing to the investigator. A copy of the initial IRB approval letter will be provided to the sponsor before commencement of this study.

All subjects for this study will be provided a consent form describing this study and providing sufficient information for subjects to make an informed decision about their participation in this study. The consent form will be submitted with the protocol for review and approval by the IRB. The consent of a subject, using the IRB-approved consent form, must be obtained before that subject is submitted to any study procedure. Consent will be documented as required by the IRB.

13 Literature References

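### The controlled phase spans two hospitals, but the planned analyses have no site term and the plan does not say whether allocation used site or how many first-site participants were randomised

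*Combined protocol and SAP*

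**What the plan says.** Section 11.2 sets the total, "The overall target for recruitment is 100 participants", and splits it by hospital: "52 participants will be recruited for the protocol once approved by BMC (48 participants were recruited at Beth Israel Deaconess Medical Center". One group is in the past tense and the other in the future, so the sites recruited one after the other.

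Section 5 gives the order of work: "The intervention will be trialed for feasibility and then tested against a small waitlist condition control arm". It then says "Phase 1 of the study was completed at its initial site at Beth Israel Deaconess Medical Center" and "Phase 2 was also started at the previous sight and will be completed at Boston Medical Center". The phases are not formally defined. Read together, these sentences make Phase 2 the comparison with waitlist, with the hospital changing partway through it.

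On allocation, the Randomization row of the Section 9 table says only "Once baseline assessments are complete, study staff randomize participant into MILO or waitlist condition". Section 5 gives the ratio: "Participants will be randomly assigned to either receive MILO (50%) or the waitlist condition (50%) in a cross over design". The Section 2 summary agrees, but Section 11.2 expects a control group smaller than the active group and gives no numbers.

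On analysis, Section 11.3 says "The outcomes of interest will be compared between the intervention and waitlist groups". It uses odds ratios for treatment seeking by the individual with psychosis (IP) and group-by-time repeated measures ANOVAs for the caregiver outcomes. No site factor, stratum or by-site summary is mentioned, and the section does not say which of the 48 first-site participants enter the comparison.

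**The concern.** Because recruitment was sequential, site stands for hospital, calendar period and local services together. IP engagement plausibly depends on which services are within reach, so site is a candidate predictor of the outcome that Section 11.2 calls primary. If the arms differ in site mix, part of any site difference enters the MILO-waitlist contrast. Even with balanced arms, between-site variation stays in the error term.

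The second issue is who is being compared. A feasibility phase was completed at the first hospital before the controlled test, so some of the 48 may never have been randomised. Counting them in the MILO arm would tie arm to site by construction. A different allocation ratio at each hospital would do the same.

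The stake is the effect size estimate that Section 11.2 says will inform a later trial. Feasibility, the primary outcome in Section 4.2.1, is also affected: one combined figure would not show whether delivery held up after the move.

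**Working it through.** **Plan's own figure.** 48 + 52 = 100, as stated in Section 11.2. The plan gives no alpha, power, effect size, SD or event rate, so there is no power calculation to reproduce.

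**Inputs.** From the documents: 48 and 52 by site, and 50:50 allocation (Sections 2 and 5). Assumed: all 100 were randomised, 50 per arm, without regard to site; the site differences below are also assumptions, because the documents give no data on them.

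**1. Chance imbalance in site share.** Let k be the number of first-site participants in the MILO arm, hypergeometric with arm totals fixed. The gap in share is (2k − 48)/50.
- Var(k) = 50 × 0.48 × 0.52 × 50/99 = 6.30, so SD(k) = 2.51 and the SD of the gap is 2 × 2.51/50 = 0.100.
- P(gap ≥ 10 points), in practice 27 v 21 or worse: 32%.
- P(gap ≥ 20 points), 29 v 19 or worse: 7%.
- If only 10, 20 or 30 of the 48 were randomised, P(gap ≥ 10 points) is 30%, 43% or 25%. The sequence is uneven because the counts are discrete.

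**2. Effect on IP engagement.** Shift = gap in site share × site difference.
- Assumed 20-point site difference: 0.10 × 0.20 = 0.02, or 2 points per 10 points of imbalance.
- SE of the arm difference = √(2p(1 − p)/50). For assumed p of 30% and 40% this is 9.2 and 9.8 points, so 2 points is about 0.2 SE.
- At 40% overall, removing site lowers the SE to √(2 × (0.24 − 0.48 × 0.52 × 0.20²)/50) = 9.6 points.
- As an odds ratio, with no treatment effect, 29 v 19 first-site participants and assumed site rates of 20% and 40%: MILO (29 × 0.20 + 21 × 0.40)/50 = 28.4%; waitlist (19 × 0.20 + 31 × 0.40)/50 = 32.4%; odds ratio 0.83, or 1.21 with the imbalance reversed. Site rates of 30% v 40% give 0.92; 20% v 50% give 0.77.

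**3. Effect on a continuous contrast.** With site difference g (in within-site SDs), SE = √((1 + 0.48 × 0.52 × g²) × 4/100).
- For g = 0.5 the SE is 0.206, against 0.200 with a site term.
- A 20-point imbalance with g from 0.2 to 0.5 shifts the contrast by 0.04 to 0.10 SD, or 0.20 to 0.49 SE.
- In 20,000 simulated trials with g = 0.5, type I error was 5.1% without and 5.0% with a site term. Power for an assumed 0.5 SD effect was 67.0% and 69.4%.

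**4. Systematic version.** Suppose n₀ of the 48 were unrandomised, all counted as MILO, and everyone else was split 1:1.

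| n₀ | MILO, first-site share | Waitlist, first-site share | Gap | Shift at a 20-point site difference |
|---|---|---|---|---|
| 10 | 29/55 = 52.7% | 19/45 = 42.2% | 10.5 | 2.1 points |
| 20 | 34/60 = 56.7% | 14/40 = 35.0% | 21.7 | 4.3 points |
| 30 | 39/65 = 60.0% | 9/35 = 25.7% | 34.3 | 6.9 points |

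These gaps are expected values, not chance events, and randomisation does not protect against them.

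**The case against.** The strongest reply is that sound randomisation already deals with this. The unadjusted contrast is then unbiased on average, its SE includes chance site imbalance, and type I error is about 5% either way. The gain from a site term is about two percentage points of power in a pilot that describes itself as possibly underpowered. All of that stands.

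A reader might infer that allocation ignored site. The documents do not show this: Section 9 gives no method at all. Because the sites ran in sequence, ordinary blocking or a fresh list at BMC would have roughly balanced site. The 32% applies only to unrestricted allocation.

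A reader might also infer that site strongly affects engagement. Nothing in the documents measures this. They do not describe delivery or local services at the first hospital, and describing the waitlist consultation as BMC's minimum standard of care (Section 6.2) does not show that it differed elsewhere. The 20-point difference is illustrative.

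Constant differences in level between sites cancel in the group-by-time tests and in the within-waitlist comparison. What remains is any site difference in change over time, and the engagement odds ratio, for which no baseline term is stated. Finally, the plan does not say that feasibility will be reported only in combined form; it is silent.

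The reply does not meet the possible pooling of Phase 1 participants or unequal ratios by site, because it presumes that everyone compared was randomised at a common ratio.

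**Conclusion.** The point holds at modest size. The site changed within what reads as the controlled phase, site is known for every participant, and the stated analyses do not use it. If all 100 were randomised 1:1 without regard to site, the consequence is a conditional shift of about 0.2 SE per 10 points of imbalance under an assumed 20-point site difference, plus a small loss of precision. A claim of bias on average or inflated type I error would go further than the documents and the calculations allow.

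The more serious possibility is systematic: an expected gap in site share of about 11, 22 or 34 points if 10, 20 or 30 unrandomised first-site participants were counted as MILO. The documents do not say that this will happen. They leave it open, and the conflict between a 50:50 split and a smaller control group makes it harder to rule out.

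**What to change.** In Section 11.3:
- State how many of the 48 were randomised, and limit the MILO-waitlist comparison to randomised participants. A site term alone would not make unrandomised participants comparable.
- Use a site-stratified (Mantel-Haenszel) estimate for IP engagement.
- Add site and site-by-time to the caregiver outcome models. The site-by-time term is the one that matters for the group-by-time test.
- Report arm counts and each feasibility metric by site as well as combined.

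In Section 9, first reconcile the 50:50 ratio in Sections 2 and 5 with the smaller control group in Section 11.2. Then allocate the remaining BMC participants at the agreed ratio from their own concealed permuted-block list, released after baseline is complete, and record the method used at the first hospital.

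The cost is one allocation list and one or two degrees of freedom. No new data are needed. The stratified odds ratio is conditional on site, so it estimates a slightly different quantity from the crude one, and the report should say so. Excluding unrandomised participants reduces the number compared, but they still count towards feasibility.

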11.3 Statistical Methods

Feasibility will be analyzed using the following descriptive metrics: # participants screened; # Eligible; # Enrolled; # not enrolled and corresponding reasoning # Meeting DSM-5 Adjustment Disorder criteria; Percentage of Treatment sessions completed; Treatment Satisfaction; % assessments completed; Duration of assessments.

The outcomes of interest will be compared between the intervention and waitlist groups, and also within the waitlist group (comparing the pre-post intervention changes to the pre-post waitlist time changes. Prevalence of IP treatment seeking in each group will also be analyzed via odds ratios. Secondary outcomes, i.e. changes in PCSO distress and quality of life, will be

assessed via repeated measures ANOVAs examining group-by-time changes. Similarly, hypothesized mediators of effects (MI skill proficiency and self-efficacy) will be examined via repeated measures ANOVAs examining group-by-time changes. Analyses will be conducted using SPSS software.

12 Ethics/Protection of Human Subjects

This study is to be conducted according to applicable US federal regulations and institutional policies (which are based in federal regulations, guidance, and ICH Good Clinical Practice guidelines).

This protocol and any amendments will be submitted to the Boston Medical Center and Boston University Medical Campus IRB, for formal approval of the study conduct. The decision of the IRB concerning the conduct of the study will be made in writing to the investigator. A copy of the initial IRB approval letter will be provided to the sponsor before commencement of this study.

All subjects for this study will be provided a consent form describing this study and providing sufficient information for subjects to make an informed decision about their participation in this study. The consent form will be submitted with the protocol for review and approval by the IRB. The consent of a subject, using the IRB-approved consent form, must be obtained before that subject is submitted to any study procedure. Consent will be documented as required by the IRB.

13 Literature References

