4.2 Study Outcome Measures

4.2.1 Primary Outcome Measures

Feasibility will be analyzed using the following descriptive metrics: # participants screened; # Eligible; # Enrolled; # not enrolled and corresponding reasoning; # Meeting DSM-5 Adjustment Disorder criteria; Percentage of study sessions completed; study Satisfaction; % assessments completed; Duration of assessments. A demographics questionnaire, a clinician-administered assessment containing information relevant to the DSM-5 diagnosis of adjustment disorder, and the Client Satisfaction Questionnaire will be used.

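### Section 11.3 names repeated-measures ANOVAs without saying which occasions enter, and with four assessments in one arm and five in the other, the obvious layouts either cannot be fitted or leave hypothesis 3 untested

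*Combined protocol and SAP*

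**What the plan says.** Section 11.3 states that changes in caregiver distress and quality of life will be "assessed via repeated measures ANOVAs examining group-by-time changes". The hypothesised mediators, MI skill proficiency and self-efficacy, "will be examined via repeated measures ANOVAs examining group-by-time changes". On software it says only "Analyses will be conducted using SPSS software" and names no procedure. It does not list the occasions in each model, define the participants analysed, or give a missing-data rule. Missed surveys appear only as a feasibility metric, the percentage of "assessments completed" (sections 4.2.1 and 11.3).

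The schedules differ by arm. Section 5 says "Those assigned to the MILO treatment condition will be assessed at 4 time points" and "Those in the waitlist condition will be assessed at 5 time points". The extra visit is the end of the waitlist. The table in section 4.2.2 gives the six caregiver scales five labels, "Baseline, Waitlist Condition, Post Intervention, 8 Week FU, 12 Week FU", and the second of these cannot exist for the immediate arm.

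Hypothesis 3 (section 11.1) places the between-arm comparison in the first six weeks. Hypothesis 4 concerns whether the waitlist arm draws level once it too has received MILO. Section 11.3 also plans a separate comparison within the waitlist arm.

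**The concern.** A classical repeated-measures ANOVA needs a complete row for each participant. This is a property of the method, not something the documents state. Naming the method without naming the occasions leaves two matters open until the data are in hand: who is deleted, and whether the group-by-time test includes the randomised comparison of treated with untreated caregivers at all.

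The second matters more. The end-of-waitlist record is the only follow-up taken while the waitlist arm is untreated. A layout without it cannot answer hypothesis 3, however complete the data. The first is a cost in precision. Section 11.2 already concedes limited power and wants an effect-size estimate for a later trial, so avoidable loss of participants is worth preventing.

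**Working it through.** **Inputs.** Four and five assessments by arm (section 5). Baseline is complete before randomisation (section 9), so losses can occur only at later visits: three for MILO, four for the waitlist arm. The total is 100 (section 11.2; 48 + 52 = 100) and allocation 50% each (sections 2 and 5), so 50 per arm. Section 11.2 also calls the control group small without giving a ratio; the percentages below do not depend on it. The documents give no miss rate, alpha, power or effect size, and so no calculation to reproduce. Assumed here: each follow-up is missed with probability q from 5% to 30%, a standardised difference of 0.5, and two-sided 5% significance.

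**Step 1: what each layout keeps, visits missed independently.**

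| Occasions in the ANOVA | MILO complete | Waitlist complete | Untreated follow-up included? |
|---|---|---|---|
| All five | none | (1−q)^4 | model cannot be fitted |
| Four common to both arms | (1−q)^3 | (1−q)^3 | no |
| Baseline and first post-baseline visit | 1−q | 1−q | yes |

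Four common occasions against two occasions, the same in each arm:

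- q = 5%: 0.95^3 = 86% against 95%
- q = 10%: 0.90^3 = 73% against 90%
- q = 20%: 0.80^3 = 51% against 80%
- q = 30%: 0.70^3 = 34% against 70%

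**Step 2: precision.** For two equal groups of n, power is approximately Φ(0.5·√(n/2) − 1.96). With no loss, n = 50 gives Φ(2.50 − 1.96) = 0.71. At q = 10%, n = 36.5 gives 0.57 and n = 45 gives 0.66. At q = 20%, n = 25.6 gives 0.43 and n = 40 gives 0.61. These are powers for any two-group comparison of that size; the four-occasion layout would still not be testing hypothesis 3.

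**Step 3: when loss is unequal.** With independent misses, neither workable layout in the table loses more from one arm by visit count. If people instead drop out for good at a steady rate, a waitlist participant must pass four visits to reach the last survey and a MILO participant three. The four common occasions then keep 0.90^3 = 73% of MILO and 0.90^4 = 66% of waitlist at 10% per visit, or 51% and 41% at 20%. Loss could also run the other way: section 9 sends the MILO post-intervention survey once the intervention is completed, but the end-of-waitlist survey when the waiting period ends.

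**Step 4: bias.** A simulation (4,000 runs, 50 per arm, correlation 0.5, dropout depending on the previous score at roughly 8–10% per visit, true first-period effect −0.50) gave −0.485 when completion of all visits was required, with 38.7 and 35.1 participants kept on average. Two occasions alone gave −0.495, with 44.8 kept in each arm. The standard deviations of the estimates were 0.234 and 0.212, so the variance was (0.234/0.212)² = 1.22 times as large. In this scenario the cost is mainly precision.

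**Step 5: measures that differ.** The role play has two occasions for MILO and three for waitlist. The MI Skills Questions are scheduled at baseline and post-intervention only, so the arms match but there is no untreated follow-up. The Change Questionnaire has no baseline.

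**The case against.** The strongest reply is that a group-by-time ANOVA can fit. Hypothesis 3 needs only baseline and one follow-up per arm; that two-by-two layout suits both schedules and favours neither arm by visit count. The within-waitlist comparison uses one arm and also fits. A treated-versus-treated comparison is not itself a flaw, because hypothesis 4 asks for one. All of this stands. It shows that a workable layout exists, not that the plan chose it. Visits could also be lined up by order, filling four columns in both arms, but the same column would then hold different occasions in each arm, and the overall test would mix treated-versus-untreated with treated-versus-treated differences.

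A reader might infer that the ANOVA will discard more waitlist than MILO participants because that arm has one more survey to miss. The documents do not support this. It depends on the layout and the dropout pattern, and the different survey triggers could make MILO the arm that loses more. A reader might also infer that the randomised comparison will be biased. Complete cases can be a selected group, but no document shows that they will be, and the simulated scenario produced little bias.

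Finally, the weight is limited. Feasibility is the primary outcome, treatment seeking is analysed by odds ratios, and section 11.2 aims only at a rough effect size.

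**Conclusion.** The concern holds as a gap in specification with a foreseeable cost. The occasions are not stated. One natural layout is impossible and another leaves out the comparison that hypothesis 3 needs; both conclusions follow from the schedules and the complete-row requirement alone. The two-occasion layout that would work is not written down.

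The size of the precision loss rests on assumed miss rates. At 10% it is the difference between keeping 73% and 90% of each arm; at 20%, between 51% and 80%. Unequal loss by arm is conditional and its direction is not fixed. Bias is possible but not demonstrated. The point concerns secondary outcomes and mediators, and it should be corrected because the correction is cheap.

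**What to change.** Replace the ANOVAs in section 11.3 with a baseline-adjusted linear mixed model (SPSS MIXED) using all available records from everyone randomised, and state the occasions for each hypothesis.

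- **Hypothesis 3.** Recode occasions so that the first post-baseline occasion is MILO post-intervention in one arm and end of wait in the other, and name the difference between arms at that occasion as the contrast. The protocol's own labels would leave an empty MILO cell at end of waitlist. Report actual time since randomisation for this occasion by arm, because the two surveys have different triggers, and state whether MILO participants who do not finish the sessions are sent the survey.
- **Hypothesis 4.** Compare the post-intervention, 8-week and 12-week records of the two treated groups separately, and describe the result as a catch-up comparison, not as evidence of MILO's effect.
- **Exceptions.** Say how the MI Skills Questions and the Change Questionnaire will be analysed, since one lacks an untreated follow-up and the other a baseline.
- **Sensitivity analysis.** The mixed model assumes data missing at random, which fails if current distress causes a survey to be skipped. Repeat the hypothesis 3 contrast with missing scores shifted by a stated range of amounts in each arm.

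The cost is SAP wording and one added sensitivity analysis, with the same software and measures.
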